6 months thereafter, if part of routine clinical assessment. Effectiveness measures will only be collected for patients receiving Humira.

Serious adverse events (SAE) and adverse events of interest will be recorded throughout the patient's participation in the registry or direct to HCP process and/or until 70 days following discontinuation of Humira/UMIRA administration have elapsed (which ever period is longer).

Adverse events of interest for this Registry include:

- Serious opportunistic infections, e.g., invasive fungal infections and TB
- Lymphoma including hepatosplenic T-cell lymphoma; leukemia, non-melanoma skin cancer (NMSC)
- Other malignancies (excluding lymphoma, leukemia and NMSC which are recorded separately)
- Immune reactions including lupus, lupus-like reactions and serious allergic reactions
- Congestive heart failure (CHF)
- Cerebrovascular accident (CVA)
- Myocardial infarction (MI)
- CNS demyelinating disorders (including Multiple Sclerosis and Guillain-Barré syndrome)
- Hepatic events that are serious or lead to permanent discontinuation of Humira (e.g., persistent liver function test abnormalities, acute liver failure and other serious hepatic events)
- Hematologic events that are serious or lead to permanent discontinuation of Humira (e.g., Aplastic anemia, Granulocytopenia, Granulocytes maturation Arrest, Leucopenia, Neutropenia, Pancytopenia and Thrombocytopenia)
- Worsening or new onset of Psoriasis
- Vasculitis

- Diverticulitis
- Intestinal perforation
- Occurrence of symptomatic intestinal obstruction
- Events leading to premature discontinuation of HUMIRA

Information on all concomitant medications will be captured at the time of enrollment into the Registry. Information on medications taken for CD (including dose changes) and a complete list of all medications taken at the time of a serious adverse events or adverse events of interest will be collected throughout the Registry.

This is a global registry being conducted in the US, Europe, Canada, South Africa, New Zealand and Australia and as such there are multiple local product labels. In Europe, Humira is registered for patients with severe Crohn's disease, while in the other regions it is registered for patients with moderate to severe disease. This protocol has been designed to accommodate all product labels.

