7.0 Adverse Events/Adverse Event Reporting

The physician will monitor each patient for serious adverse events and adverse events of interest throughout the patient's participation in the registry or direct to HCP process, and/or until 70 days following discontinuation of Humira administration have elapsed (whichever period is longer). The physician will assess and record any serious adverse event and adverse events of interest in detail including the date of onset, description, severity, time course, duration and outcome (when known), relationship of the adverse event to drug, an event diagnosis, if known, and any action(s) taken. For SAEs not considered "probably related" to registry drug, the physician will provide another cause of the event. Serious adverse events or adverse events of interest, whether in response to a query, observed by site personnel, or reported spontaneously by the patient will be recorded. Information about any concomitant medications taken at the time of the SAE or the adverse events of interest will be collected. For all adverse events of interest, the physician must pursue and obtain all the above mentioned information in order to adequately determine the outcome of the AE and to assess whether it meets the criteria for classification as an SAE as well as to determine a causal relationship.

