7.4 Adverse Event Collection Period

Serious adverse events and adverse events of interest will be reported to AbbVie from the time the physician obtains the subject's initial authorization to use and disclose information (or the subject's informed consent) throughout the patient's participation in the Registry, or direct to HCP process, and/or until 70 days following discontinuation of Humira administration have elapsed (whichever period is longer). A medical event that occurs after a patient discontinues the registry that is considered to be related to the patient's exposure to Humira will be reported via standard post-marketing reporting practices.

In the event Humira therapy is interrupted, SAEs and adverse events of interest will be collected throughout the interruption. If treatment with adalimumab is permanently discontinued for any reason, the reason will be recorded and the patients should be encouraged to remain in the registry for the full 6 years so important safety information can be obtained.

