7.7 Data Collection Procedures for Patients Who Re-enroll in the Registry

For patients who re-enroll in the registry, registry physicians will document any hospitalizations, surgeries, and any adverse event of interests as defined in Section 7.1.2. The physician will assess and record the date of onset (where known) and description of the event. These events will be reported via eCRF from the time of initial registry discontinuation through the date of re-enrollment, irrespective of any treatment interruption, any changes in treatment, or discontinuation of adalimumab.

The use of other medications used to treat CD and the stop and the restart dates for Humira, as applicable, from the time of initial registry discontinuation through the date of re-enrollment will be collected.

Effectiveness data will not be collected during the timeframe when the patient was not participating in the registry.

For visits occurring after re-enrollment, registry physicians will resume data collection in the eCRF process as outlined in the protocol. The duration of follow-up includes the time from initial registry consent up to 6 years.

7.8 Data Collection Procedures for Patients Who Participate in the Direct to HCP Process

For patients participating in the direct to HCP process, HCPs will document any hospitalizations or surgeries and any adverse event of interest as defined in Section 7.1.2 annually via a paper questionnaire or EDC. The HCP will assess and record the date of onset (where known), and description of the event. The use of other medications used to treat CD, and the start and stop dates for Humira will be collected on an annual basis.

These events will be reported to AbbVie from the time of initial registry consent up to 6 years, irrespective of any treatment interruption, any changes in treatment, or discontinuation of adalimumab.

Effectiveness data will not be collected as part of the direct to HCP process.

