10.5 Safety Analyses

For the Registry Safety Population, treatment-emergent SAEs and adverse events of interest will be summarized. Treatment-emergent SAEs and adverse events of interest are defined as: (1) new events that begin either on or after the first dose of Humira through the last dose of Humira plus 70 days; or (2) increase in severity of ongoing SAEs that had occurred before the first dose date of Humira. The number and percent of patients experiencing SAEs and adverse events of interest will be tabulated by body system and Medical Dictionary for Drug Regulatory Activities (MedDRA[®]) preferred term. The percent of patients will be presented with 95% confidence intervals. In addition, summary of SAEs and adverse events of interest by severity and relationship to registry drug will be presented.

The event rate of SAEs and of each adverse event of interest per 100 patient year of observation will be presented. Event rates will be presented with 95% confidence intervals. For patients enrolled from a prior CD study, the total number of SAEs and adverse events of interest will include the events reported during their participation in the previous study plus any events reports during the Registry.

In addition, Observational AEs: SAEs and AEs of interest occurring from the first dose of Humira in the registry through the last contact including re-enrollment period and during the HCP process will be tabulated.

For the 'Episodic Dosing' Population, following analyses will be provided:

- Summary of SAEs and AEs of special interest will be provided for patients with episodic dosing and without episodic dosing.

- Summary of SAEs and AEs of special interest will be provided before the treatment interruption and after the treatment interruption for patients with episodic dosing.
- For each SAE and AE of special interest, and each episodic dosing, a shift table to summarize number and percentage of patients who have the event or not before the treatment interruption and after the treatment interruption.

For the Re-enrollment Safety Population, the number and percent of patients experiencing SAEs and AEs of interest during the re-enrollment period will be tabulated by body system and MedDRA preferred term. In addition, the number and percent of patients experiencing SAEs and AEs of interest collected between registry discontinuation and re-enrollment based on a retrospective review of their patient records will be tabulated separately.

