For HCP Safety Population, the number and percent of patients experiencing SAEs and AEs of interest collected on HCP questionnaire during the HCP process will be tabulated by body system and MedDRA preferred term.

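### SAEs are promised and tabulated for the direct to HCP process, but the protocol's collection lists for it leave out SAEs with no admission, surgery or listed event

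*Protocol*

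**What the plan says.** Three sections of the protocol place SAE capture inside the direct to HCP process. Section 6.0: "Serious adverse events (SAE) and adverse events of interest will be recorded throughout the patient's participation in the registry or direct to HCP process". Section 7.0 sets out a monitoring duty "for serious adverse events and adverse events of interest throughout the patient's participation in the registry or direct to HCP process". Section 7.4 has SAEs and events of interest reported to the sponsor "throughout the patient's participation in the Registry, or direct to HCP process".

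Section 10.5 plans three outputs that use SAEs collected after a patient has left the registry:

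- a table of observational SAEs and events of interest "through the last contact including re-enrollment period and during the HCP process will be tabulated";
- a table limited to patients followed through the direct to HCP route, about which the section states: "the number and percent of patients experiencing SAEs and AEs of interest collected on HCP questionnaire during the HCP process will be tabulated";
- for re-enrolled patients, a separate table of SAEs and events of interest from the retrospective chart review of the gap between discontinuation and re-enrollment.

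The collection instructions are narrower. Section 7.8: "HCPs will document any hospitalizations or surgeries and any adverse event of interest as defined in Section 7.1.2 annually". It adds CD medication and Humira start and stop dates, and asks for onset date and a description of each event. The questionnaire description in Section 6.0 and note a to Table 1 give the same list. For the gap before re-enrollment, Section 7.7 says "registry physicians will document any hospitalizations, surgeries, and any adverse event of interests as defined in Section 7.1.2". None of these places names SAEs or death.

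**The concern.** The sections that state the duty and the analysis refer to SAEs. The sections that tell the person filling in the form what to write down refer to a shorter list. If the form follows the shorter list, some SAEs will never reach the database, and no later analysis document can restore them.

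This matters because the primary objective is long-term safety, and Section 4.0 says the follow-up procedures for patients who discontinue were added to maximize the safety information collected. A table headed SAE that rests partly on a form without an SAE item would understate SAEs for the HCP period. In the through-last-contact table a reader could not tell which part of the follow-up had full capture.

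**Working it through.** The point depends on no figure in the plan, so the check sets the passages side by side.

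**Step 1. Does the collection list cover the SAE definition?** Section 7.1.3 has nine criteria. Against the list in Section 7.8:

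| Criterion in 7.1.3 | Route in the HCP process |
|---|---|
| Hospitalization; prolongation of hospitalization | hospitalization item (2 criteria) |
| Congenital anomaly; spontaneous abortion; elective abortion | no item in 7.8; only pregnancy reporting by the site under 7.6, for pregnancies up to 150 days after the last dose (3 criteria) |
| Death; life-threatening event; disability; important medical event | no item of their own; caught only if the event is also an admission, a surgery or a listed event (9 − 2 − 3 = 4 criteria) |

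These are counts of criteria, not of events. Many events under the last four criteria will also be an admission or a listed event such as myocardial infarction, stroke, malignancy or perforation. The list is nevertheless not equivalent to the SAE definition. Section 7.1.3 itself allows for an important medical event without death or hospitalization.

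**Step 2. Does another duty or source fill the gap?**

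- *Sections 7.0 and 7.4.* These still bind a registry physician who completes the questionnaire. But Section 6.0 lets the patient's current HCP complete it instead, and says that an HCP is not a participating investigator and only fills in an annual form. For that person the list is the whole instruction.
- *Post-marketing reporting (Section 7.4).* It applies to "A medical event that occurs after a patient discontinues the registry that is considered to be related to the patient's exposure to Humira". Unrelated SAEs, or SAEs not recognised as related, do not use this route.
- *Vital status and death index matching (Section 6.5).* This can find deaths. It takes place at the end of the six-year period, and the matching is for patients lost to follow-up. The protocol neither asks for the cause of death nor says that these deaths enter the Section 10.5 tables.

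**Step 3. Which outputs are touched?**

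- *HCP Safety Population table:* SAEs are under-ascertained, but the table stands alone and names its source.
- *Through-last-contact table:* it combines registry time, with full SAE capture, and HCP time, with partial capture, under one heading. This is the main problem.
- *Gap table:* Sections 6.0, 7.0 and 7.4 cover participation in the registry or the HCP process, and the gap is neither, so they set no SAE duty there. The only tension is between the SAE label in Section 10.5 and the list in Section 7.7. Deaths are not at issue, because patients who re-enroll are alive.
- *Treatment-emergent analyses:* Section 10.1 limits the Registry Safety Population to data collected during the registry, so these are largely unaffected.
- *Lymphoma:* it is an event of interest and therefore on the HCP list. The sample size in Section 10.7 rests on lymphoma and is not affected.

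**The case against.** Four arguments can be made for the plan.

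*The form is not shown.* The questionnaire is not among Appendices A to G. Section 6.0 describes its focus, which need not be a complete list, and Section 10.5 speaks of SAEs collected on it. The form may therefore carry an SAE item. This stands to the extent that no one can conclude from the protocol that the form lacks one. It does not remove the conflict: Section 7.8 and note a to Table 1 state what is collected, and neither includes SAEs.

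*Reduced capture is deliberate.* The simplified questionnaire is for patients who decline full data collection or who left for other reasons, and the HCP and gap data are tabulated separately. This is a fair defence of the two separate tables. It does not cover the through-last-contact table, which has no such limit, or the SAE wording in Sections 6.0, 7.0 and 7.4.

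*Most serious events are caught anyway.* Admissions and the major events are listed, so the loss is partial. This stands, and it limits the severity.

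*There is no breach of the 24-hour rule.* A reader might infer that an annual paper form violates the 24-hour SAE reporting in Section 7.1.3. The documents do not support that. The clock starts when the study site is notified, an outside HCP is not a study site, and Section 7.8 also allows electronic entry.

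**Conclusion.** The protocol is wrong as written, through an internal contradiction of minor to moderate severity. The SAE promise in Sections 6.0, 7.0 and 7.4 and the SAE tables in Section 10.5 do not match the collection lists for the HCP process in Section 7.8, Section 6.0 and note a to Table 1. SAEs without an admission, surgery or listed event are not reliably captured when an outside HCP completes the form. The label of the gap table is a separate and smaller mismatch with Section 7.7.

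The conclusion assumes that the questionnaire follows the lists in the protocol. The number of missed SAEs cannot be derived. A reader might try to bound it from the attrition in Section 10.7: 5,000 × 6 = 30,000 patient-years if no one left, less the planned 16,230, gives 13,770, or 45.9%, after dropout. That is not the share of follow-up in the HCP process. The attrition comes from two earlier trials, patients are now encouraged to stay after stopping Humira, and the protocol gives neither the rate of consent to the HCP process nor the fraction of SAEs that fall outside the list. The effect is probably modest. The documents do not support a wider claim that the registry's safety results, its lymphoma assessment or its sample size are compromised.

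**What to change.** 1. Add death (date and cause) and any other event meeting Section 7.1.3 to Section 7.8, note a to Table 1 and the HCP questionnaire.
2. Add any other event meeting Section 7.1.3 to the gap review in Section 7.7.
3. State in Section 10.5 that deaths found under Section 6.5 enter the through-last-contact table.

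If the items cannot be added, label the HCP and gap tables in Section 10.5 by what is actually collected (hospitalizations, surgeries, events of interest) and show them separately from registry SAEs. Keep the SAE wording in Sections 6.0, 7.0 and 7.4 for registry physicians, since deleting it would remove a duty that still applies when they complete the questionnaire.

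The cost is one or two extra items on an annual form, one on the chart review, and matching wording. Relabelling alone adds no work at sites, but deaths outside the list would then still not be asked for in the HCP process.

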6.4.8 Adalimumab Treatment and Dosing Changes

The participating physician will provide the patient a prescription for HUMIRA, along with instructions for appropriate use. At subsequent protocol-defined study visits the physician will collect the start and stop dates, any dose interruptions and reason for the dose interruption that may have occurred since the last study visit. The dose, dates of administration, any dose interruptions and the reason for the interruption will be captured in the source documents and eCRFs.

Dose interruptions for the study will be defined as patients missing > 1 dose. The reason(s) for interruptions will be captured on the eCRF.

Most clinical data associated with this study will be collected and reported electronically (eCRF) via a web address and secure password. Patient questionnaires will be completed on forms formatted for fax scanning. The site will fax or email completed forms into the designated Study Help Desk.

At the enrollment visit, the physician will complete the Enrollment eCRFs by obtaining and recording all available required information, including visit date, demographic data, concomitant diseases and concomitant medications.

At subsequent visits corresponding to the schedule of assessments ([Table 1](#)), the physician will complete the appropriate eCRF by obtaining and recording all available information. Since this is an observational study conforming to usual clinical practice, data from subject visits that most closely correspond to the schedule of assessment at Months 3, 6, 9, 12, 18, 24, 30, 36, 42, 48, 54, 60 66 and 72 will be accepted. For example, if a patient visits the physician's site at Month 5, this is close to the protocol-defined 6-month study

visit, so data can be collected for this visit. If the same patient unexpectedly returns for a visit to the physician's site at a date closer to the 6-month visit, no further PRO data needs to be collected since the data was previously collected. Safety data that meets the criteria for collection should be collected regardless of protocol-defined study visits.

If a patient completes the 6-year observation period study completion of eCRFs should be completed.

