7.1.2 Adverse Events of Interest

The physician will monitor each patient for clinical and laboratory evidence for adverse events of interest at the Baseline visit and on a routine basis throughout the registry.

Adverse events of interest for this registry include:

- Serious opportunistic infections e.g., invasive fungal infections and TB
- Lymphoma including hepatosplenic T-cell lymphoma; leukemia, non-melanoma skin cancer (NMSC)
- Other malignancies (except lymphoma, leukemia and NMSC)
- Immune reactions including lupus, lupus-like reactions and serious allergic reactions
- Congestive heart failure (CHF)
- Cerebrovascular accident (CVA)
- Myocardial infarction (MI)
- CNS demyelinating disorders (including Multiple Sclerosis and Guillain-Barré syndrome)

- Hepatic events that are serious or lead to permanent discontinuation of Humira (e.g., persistent liver function test abnormalities, acute liver failure and other serious hepatic events)
- Hematologic events that are serious or lead to permanent discontinuation of Humira (e.g., Aplastic anemia, Granulocytopenia, Granulocytes maturation Arrest, Leucopenia, Neutropenia, Pancytopenia and Thrombocytopenia)
- Worsening or new onset of Psoriasis
- Vasculitis
- Diverticulitis
- Intestinal perforation
- Occurrence of symptomatic intestinal obstruction
- Events leading to premature discontinuation of Humira

During the course of the registry additional adverse events of interest may be identified by AbbVie. Updates to the adverse events of interest will be maintained and collected through the eCRF system. Sites will be trained on all updates to the eCRF system.

The physician will assess and record any additional information on the adverse event of interest in detail on the Adverse Events of Interest eCRF.

The physician will assess all reported adverse events of interest for seriousness and follow the requirements/timelines for reporting any AEI that fulfills the criteria of an SAE, as defined in Section [7.1.3](#).

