10.0 Statistical Methods and Determination of Sample Size

10.1 Statistical and Analytical Plans

Analyzable Populations:

Safety Populations During the Registry:

The Registry Safety Population consists of all patients who received at least one dose of Humira (adalimumab) in the Registry. This will be the population for safety analyses in the Registry and include safety data collected during the Registry only.

The "Episodic Dosing" Population will consist of patients in the Registry Safety Population who:

- discontinue Humira (adalimumab) at least once for more than 70 days and receive at least one dose of adalimumab after the treatment interruption,
- do not receive any other biologics during the treatment interruption and,
- provide data before and after Humira (adalimumab) treatment interruption period(s)
- and include safety data collected during the Registry only.

For patients previously treated with commercial Humira before enrollment into the Registry, Day 1 of adalimumab treatment will be the 1st day of Humira therapy, i.e., before enrollment into the Registry. Detailed information on concomitant medications, safety and effectiveness between the 1st dose of Humir and enrollment into the Registry will be available for these patients.

Re-enrollment Safety Population:

The Re-enrollment Safety Population consists of all patients who were discontinued from the Registry due to prior protocol withdrawal criteria (i.e., patients who have discontinued Humira therapy) or discontinued for other reasons and re-consent to participation in the Registry. This will be the population for safety analyses of data collected during the re-enrollment period.

For patients that re-enroll in the Registry, safety information collected between registry discontinuation and re-enrollment based on a retrospective review of their patient records will be analyzed separately.

HCP Safety Population:

The HCP Safety Population consists of all patients that decline re-enrollment to participation in the Registry or who have discontinued from the Registry for other reasons and consent to data release for the completion of a simplified HCP questionnaire in the direct to HCP process. This will be the population for safety analyses of data collected on HCP questionnaire.

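### The before/after-interruption safety comparison in Section 10.5 can shift in either direction with no change in risk, because triggering events, gap events and period length are not handled

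*Protocol*

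**What the plan says.** Section 10.1 defines the Episodic Dosing Population as patients in the Registry Safety Population who, among other conditions, "discontinue Humira (adalimumab) at least once for more than 70 days and receive at least one dose of adalimumab after the treatment interruption". They must also have data on both sides of the gap.

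Section 10.5 plans two within-patient displays for them. The first is a summary that "will be provided before the treatment interruption and after the treatment interruption for patients with episodic dosing". Its measure is not named. The second, for each event and each episode, is "a shift table to summarize number and percentage of patients who have the event or not before the treatment interruption and after the treatment interruption".

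Other sections bear on these displays:

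- Section 7.1.2 lists "Events leading to premature discontinuation of Humira" among the adverse events of interest.
- Section 7.4 states: "In the event Humira therapy is interrupted, SAEs and adverse events of interest will be collected throughout the interruption".
- Section 6.4.8 has start and stop dates and interruptions recorded, and adds: "The reason(s) for interruptions will be captured on the eCRF".
- Section 10.5 counts events as treatment-emergent up to 70 days after the last dose. It plans rates per 100 patient-years with 95% confidence intervals among the overall safety analyses, but does not repeat them for the episodic displays.

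**The concern.** A before/after table invites the reader to compare its two columns. Three features of the stated design can move those columns apart when nothing about the drug's risk has changed.

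1. **Triggering events.** If an SAE or event of interest leads to the interruption, it comes before the gap and is counted there unless a rule says otherwise. Section 10.5 has no such rule.
2. **Gap events.** Every qualifying gap exceeds 70 days, so each contains a full 70-day carry-over window. Section 10.5 does not say whether events in that window count as before, or where later gap events go. A two-state table has no cell of its own for them.
3. **Exposure.** The shift table counts patients with or without the event. A longer period collects more such patients at the same rate.

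Entry also requires resumption of Humira, so patients whose event ended treatment for good are left out. That pulls the before column the other way. At stake is whether this table, in a long-term safety registry run under a post-marketing commitment (Section 4.0), says anything usable about stopping and restarting.

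**Working it through.** The protocol states no figure for this comparison, so there is none to reproduce. All inputs below are assumptions, chosen so that true risk is the same before and after.

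**Closed form.** Let λ be the event rate (0.10 per patient-year), f the share of gaps triggered by an event, and Tb and Ta the lengths of the two periods in years.

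- Before % = f + (1 − f)(1 − exp(−λTb))
- After % = 1 − exp(−λTa)
- Before rate = λ + f/Tb; after rate = λ

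Equal periods of 1.5 years: 1 − exp(−0.15) = 0.1393.

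| f | Before % | After % |
|---|---|---|
| 0 | 13.9 | 13.9 |
| 0.10 | 0.10 + 0.90 × 0.1393 = 22.5 | 13.9 |
| 0.25 | 0.25 + 0.75 × 0.1393 = 35.4 | 13.9 |
| 0.50 | 0.50 + 0.50 × 0.1393 = 57.0 | 13.9 |

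Unequal periods, Tb = 1 and Ta = 4, f = 0.10: before = 0.10 + 0.90 × 0.0952 = 18.6%; after = 1 − exp(−0.40) = 33.0%. The sign has reversed. As rates, the same case gives 10 + 100 × 0.10/1 = 20.0 versus 10.0 per 100 patient-years. Patient-years therefore correct for length but not for the trigger; both need attention.

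**Simulation.** The closed form fixes f and ignores selection on resuming. A simulation of 200,000 patients over 6 years adds it. Assumed inputs: 10 events per 100 patient-years; probability 0.5 that an event stops treatment; other-cause stopping 0.25 per patient-year; gap of 70 days plus an exponential time with mean 0.5 years; probability 0.5 of resuming after a non-event stop.

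| Probability of resuming after an event stop | Before % | After % | Before rate | After rate | Before rate without triggers |
|---|---|---|---|---|---|
| 0.8 | 31.2 | 18.5 | 17.2 | 10.1 | 5.0 |
| 0.5 | 24.4 | 18.2 | 13.5 | 9.9 | 5.1 |
| 0.1 | 12.8 | 18.5 | 7.0 | 10.1 | 5.0 |
| 0 | 9.3 | 18.2 | 5.1 | 10.0 | 5.1 |

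With no event-triggered stops, the columns agree (17.8% versus 17.9%). Across the no-change scenarios run, including event rates of 5 and 20 per 100 patient-years, 11% to 18% of all events fell in the gap.

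**Which handling of triggers works.** Dropping the trigger from the before column only gives 9.1% to 9.3% before against 18.2% to 18.5% after, an artificial doubling. If events that end a course are set aside on both sides, the remaining rate is 10 × (1 − 0.5) = 5 per 100 patient-years in either period, provided an event is as likely to stop treatment after restart as before. The last column of the table shows this value on the before side whatever the chance of resuming.

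**The case against.** The strongest reply is that these are descriptive displays for one subgroup. Section 10.2 plans descriptive statistics, and Section 10.5 attaches no test and states no purpose for the comparison. Period boundaries and allocation of events are commonly left to the SAP. That holds for the detail of the windows. It does not cover what the protocol itself fixes, namely two states and, for the shift table, patient percentages. Elsewhere it is more specific: Section 10.4 sets timing rules for episodic efficacy data, and Section 10.5 tabulates the interval between discontinuation and re-enrollment separately.

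Several stronger readings are tempting and should be resisted.

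- A reader might infer that the table must make re-treatment look safer. It need not. Selection on resuming and a longer after period both push the other way, and the after period can contain events that end the second course.
- A reader might infer that gap events are lost from the plan. They are not. The Observational AE table in Section 10.5 runs from the first registry dose to last contact and includes them. The treatment-emergent window covers the whole gap or its first 70 days, depending on how last dose is read.
- A reader might infer that the protocol expressly counts the trigger as before, or expressly excludes the first 70 days of the gap. It says neither. The first follows from chronology; the second is unresolved.

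The share of gaps triggered by an event is also not given. Interruption for pregnancy, which Section 7.6 does not class as an adverse event, is foreseen. Because the shift table is built event by event, the share relevant to any one row is smaller than the all-event share.

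**Conclusion.** The point holds as a problem of interpretability, not as a bias of known sign. As written, the before/after comparison mixes the risk on treatment with three other things: how often an event causes the gap, how often patients resume after such an event, and how long each period lasts. Under unchanged risk, the illustrations run from 57.0% versus 13.9% to 9.3% versus 18.2%. These rest on the assumed inputs shown and are not estimates for this registry; the size cannot be computed from the protocol. A claim that the plan gives false reassurance about restarting would go further than the text allows. The lymphoma sample size and the overall safety tables are unaffected.

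**What to change.** In Section 10.5, for the Episodic Dosing Population:

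1. Define three analysis periods: before (through 70 days after the last pre-gap dose), during (beyond 70 days until restart), and after (from restart, with the same 70-day rule at the end of that course).
2. Report events per 100 patient-years with 95% confidence intervals in each period, alongside the shift table.
3. Flag events recorded as the reason for an interruption or discontinuation. Show results with and without them, treated the same way before and after. Do not remove them from the before period only.

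The cost is wording, an added period and slightly more analysis work. Treatment dates and reasons for interruption are already collected (Section 6.4.8), as is the reason for permanent discontinuation (Section 7.4). The downside is small counts per period, especially for rare events, which the confidence intervals will show.
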